Three ERPs will be measured: 1) the late positive potential (LPP), 2) the reward positivity (RewP), and 3) the P1. The LPP is a measure of sustained attention to affective stimuli generated by a network of brain areas involved in emotional processing and is larger for positive than neutral stimuli (Y. Liu, Huang, McGinnis-Deweese, Keil, & Ding, 2012; Schupp et al., 2000). It is blunted in depression (MacNamara, Kotov, & Hajcak, 2016; Weinberg, Perlman, Kotov, & Hajcak, 2016) but increases with behavioral therapies (Garland, Froeliger, & Howard, 2015; Leutgeb, Schäfer, & Schienle, 2009), suggesting that it indexes a state-related abnormality. The RewP is a measure of initial responsiveness to reward generated by the ventral striatum in response to feedback indicating desirable outcomes (Carlson, Foti, Mujica-Parodi, Harmon-Jones, & Hajcak, 2011; Foti, Weinberg, Bernat, & Proudfit, 2015; Holroyd, Krigolson, & Lee, 2011; Proudfit, 2014). It is blunted during episodes of depression (Foti, Carlson, Sauder, & Proudfit, 2014; W. Liu et al., 2014) and remission (Weinberg & Shankman, 2016; Whitton et al., 2016) and prior to first-onset depression (Bress, Foti, Kotov, Klein, & Hajcak, 2013; Nelson, Perlman, Klein, Kotov, & Hajcak, 2016), suggesting that it is a trait marker of reward system vulnerability. The P1 is an index of early visual attention generated in the extrastriate cortex (Di Russo, Martínez, Sereno, Pitzalis, & Hillyard, 2002). The P1 for affectively neutral stimuli is not influenced by depression (Dai & Feng, 2011; Dai, Wei, Shu, & Feng, 2016; Zhao et al., 2015). It is included to assess whether the effects of Engage are *specific* to reward systems. Behavioral activation will be assessed with the Behavioral Activation for Depression Scale (BADS) (Kanter, Mulick, Busch, Berlin, & Martell, 2007), and additional behavioral and self-report measures of reward processing are included for hypothesis generation.

Aims and Hypotheses

Primary aim: To study target engagement of the reward system in Engage.

H1: Engage-treated participants will have greater increase in LPP and BADS from baseline to week 9, but not in RewP and P1, compared to ST-treated participants.

H2: The course of LPP will be significantly associated with the course of BADS in Engage-treated participants.

Secondary aim: To identify predictors of change in anhedonia with Engage.

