SH1: Change in LPP for each assessment interval (baseline-3 weeks, 3-6 weeks) predicts severity of anhedonia at the next assessment time (6, 9 weeks) in Engage, but not in ST participants.

SH2: Change in BADS for each assessment interval predicts severity of anhedonia at the next assessment time in Engage, but not in ST participants.

Analysis Plan

We anticipate that approximately 15% of patients will fail to comply with the treatment protocol. Therefore, we will recruit 85 depressed older adults to meet our goal of 70 participants.

Descriptive Statistics

We will use graphical methods (e.g., box-plot) to examine the distribution and outliers of each clinical and demographic variable. If distribution assumptions are violated, we will use transformations or bootstrapping. In comparisons between Engage- and ST-treated subjects, we will include in regression models any variables (e.g. antidepressant use) that are unbalanced in these groups. We will control the overall Type I error rate at 5% after adjusting for multiple comparisons using Holm's stepdown procedure.

Analyses for Primary Hypotheses

H1. Engage-treated participants will have greater increase in LPP and BADS from baseline to week 9, but not in RewP and P1, compared to ST-treated participants. We will use separate mixed-effects regression models for the dependent variables (LPP and BADS assessed at baseline and weeks 3, 6 and 9). Our model will include fixed effects for age, time, sex, antidepressant use, and other variables when they differ between groups. Higher order(s) of the time variable (e.g., quadratic, cubic, etc.) or time as a categorical variable will be investigated. A significant interaction between time and treatment group will confirm our hypotheses. Separate mixed-effects models will be constructed with RewP and P1 assessments at baseline, weeks 3, 6 and 9 as dependent variables; we expect a weak time x group interaction, if any, for these variables because RewP remains blunted even in remitted depression and P1 is unrelated to reward function. While we do not expect to have power to test non-inferiority of RewP and P1 in Engage compared to ST, the proposed analysis will offer preliminary data on lack of change over time during treatment in RewP and P1 in both treatment arms.

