Mixed-effects models will include an age-group level random intercept to account for correlation among Engage- and ST- treated participants matched by age groups. In models where repeated measures are analyzed, we will include another subject-level random intercept nested within age-group to account for correlations among repeated measures and will include a random slope parameter.

Correction for Multiple Comparisons

We will control the study-wide false discovery rate for all hypotheses using the Benjamini-Hochberg method (Benjamini & Hochberg, 1995).

Power

H1. With 35 participants in each group, we will have 80% power at an alpha=2.5% to detect a difference of greater than or equal to 0.8 standard deviations in LPP and BADS change from baseline to 9 weeks, assuming a range of intra-class correlation coefficients for repeated measures ($\rho=0.2$ to 0.5) and an attrition rate of 10%. Our estimate of power is conservative as it is based on a pre-post test of mean difference between two treatment groups, whereas our analytic plan will use repeated measures to detect difference in slopes of LPP or BADS change over time. This study is not powered to detect non-inferiority of RewP and P1 in Engage vs. ST.

H2. With 35 participants in the Engage group, we will be able to estimate the correlation between LPP and BADS with a 95% confidence interval width of 0.15-0.47 for a range of correlations (0.6-0.9).

Patient Study Participants

Subject Population

There are two treatment arms to this study. Arm 1 patient participants will be 70 older adults (age ≥ 60) with MDD, 35 per treatment group. Diagnosis will be determined by the Structured Clinical Interview for DSM-5 (SCID) (First, Williams, Karg, & Spitzer, 2015). Participants will be free of major medical comorbidities and either free of antidepressants or on a stable dose for at least 12 weeks with a plan to continue on the same dose for the duration of the study.

Arm 2 patient participants will be older adults who report significant symptoms of depression but do not meet study criteria due to insufficient symptoms and/or severity, a recent change in medication, or past psychiatric comorbidity that does not contribute significantly to the current clinical presentation. These individuals will be "practice case" participants and will receive therapy from therapists undergoing training to administer therapy for the study.

Recruitment

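### H1 is about the Engage advantage in change from baseline to week 9, but the rule confirms it on any significant time x group interaction, with the form of time left open

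*Combined protocol and SAP*

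**What the plan says.** Aims and Hypotheses states H1 as a directional claim about one interval: "Engage-treated participants will have greater increase in LPP and BADS from baseline to week 9", compared with ST. The H1 paragraph of Power is built on the same quantity. It claims 80% power at alpha 2.5% to "detect a difference of greater than or equal to 0.8 standard deviations in LPP and BADS change from baseline to 9 weeks".

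The H1 paragraph of Analyses for Primary Hypotheses plans mixed models on data from baseline and weeks 3, 6 and 9. It says that higher orders of time "or time as a categorical variable will be investigated", and then gives the decision rule: "A significant interaction between time and treatment group will confirm our hypotheses". It states no degrees of freedom, no week-9 contrast, no sign and no criterion for choosing the form of time.

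Two other places hint at a linear form. Power says "our analytic plan will use repeated measures to detect difference in slopes of LPP or BADS change over time", and Comment on Mixed-Model Analyses adds a random slope.

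On error control, Descriptive Statistics says "We will control the overall Type I error rate at 5% after adjusting for multiple comparisons", by Holm's method. Correction for Multiple Comparisons says "We will control the study-wide false discovery rate for all hypotheses using the Benjamini-Hochberg method". Neither is said to cover a choice among forms of time within one outcome.

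**The concern.** The hypothesis, the sample size and the decision rule should concern the same quantity. Here the first two concern the week-9 change, while the rule accepts any significant time x group interaction. With linear time that is a slope difference, which equals the week-9 difference only if the course is linear. With quadratic or categorical time it is a 2- or 3-df test that any departure from parallel courses can trigger. Such a test has no direction, so it cannot by itself enforce the direction in H1.

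Three things are at stake:

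- A mid-treatment difference that has gone by week 9 could confirm a week-9 hypothesis.
- Two analysts who both follow the plan could reach opposite verdicts from the same data.
- If the form is chosen by looking at models that already contain the arm difference, the type I error of the primary test exceeds its nominal level.

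**Working it through.** **Inputs from Power, H1.** 35 per group, 10% attrition (n = 35 x 0.9 = 31.5 per arm), alpha 2.5%, 0.8 SD, intra-class correlation rho = 0.2 to 0.5. **Assumptions.** Two-sided tests, compound symmetry with unit variance, large-sample Wald tests, and the courses named below. Paired figures are for rho 0.2 / 0.5.

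**Step 1: the plan's own figure.** Take 0.8 as SDs of the change score. Then 0.8 x sqrt(31.5/2) = 3.175, and 3.175 - 2.241 = 0.934, so power is 82.5% by the normal approximation. The noncentral t gives 80.7% with 31.5 per arm and 80.0% with 31. The stated 80% is reproduced, for a week-9 change contrast tested two-sided.

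**Step 2: formulas.** Let d be the Engage minus ST differences at baseline and weeks 3, 6 and 9, in SDs of a single measurement. For orthonormal time contrasts c_k, the noncentrality is (n/2) x sum of (c_k·d)² / (1 - rho). For the week-9 contrast it is (n/2) x (d9 - d0)² / [2(1 - rho)]. Critical values at 2.5% are 5.024 (1 df), 7.378 (2 df) and 9.348 (3 df).

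**Step 3: a transient effect, d = (0, 0.6, 0.6, 0).** Only the quadratic contrast is non-zero, at -0.6. Noncentrality is 15.75 x 0.36/0.8 = 7.09, or 15.75 x 0.36/0.5 = 11.34. The 3-df test is significant in 48.5 / 73.5% of trials and the quadratic 2-df test in 55.4 / 79.4%. The week-9 contrast and the slope test reject in 2.5%. With 0.3 SD in place of 0.6, the 3-df test gives 11.0 / 17.7% and the 2-df test 13 / 21%.

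**Step 4: the plan's effect size, 0.8 SD at week 9.**

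- Linear course. The linear contrast squared is 0.3556. Noncentrality is 15.75 x 0.3556/0.8 = 7.00, or 11.20 at rho 0.5, for both the slope and the 3-df test. For the week-9 contrast it is 15.75 x 0.64/1.6 = 6.30, or 10.08.
- Gain by week 3 that then holds, d = (0, 0.8, 0.8, 0.8). Slope: 15.75 x 0.288/0.8 = 5.67, or 9.07. 3-df: 15.75 x 0.48/0.8 = 9.45, or 15.12. The week-9 contrast is unchanged.

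| Course | Slope | Week-9 contrast | 3-df |
|---|---|---|---|
| Linear | 65.7 / 86.5% | 60.6 / 82.5% | 47.9 / 72.8% |
| Gain by week 3, held | 55.6 / 78.0% | 60.6 / 82.5% | 63.6 / 87.0% |

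In 1,000,000 simulated trials the three readings did not all agree on H1 in 26 / 18% (linear) and 27 / 18% (held). Slope and week-9 results counted only when they favoured Engage. If the 0.8 SD is of the change score, the rho 0.5 powers apply at any rho.

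Power also says "Our estimate of power is conservative as it is based on a pre-post test of mean difference between two treatment groups". That is true of a slope test on a linear course. It is not true of a 3-df test on a linear course, or of a slope test when the gain comes by week 3 and holds.

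**Step 5: type I error per outcome, nominal 2.5%.** The linear, quadratic and cubic contrasts are independent, so these results do not depend on rho or on a random slope.

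- Form fixed in advance, or chosen on the pooled time trend: 2.5%.
- Form chosen among models containing time x group: BIC 2.7-3.5%, AIC 3.4-4.5%. The range covers a pooled quadratic trend of 0 to 5 standard errors and, for BIC, a penalty based on 63 participants or 252 observations.
- Best of the three joint tests: 4.8%.
- Any polynomial term counts: 1 - 0.975³ = 7.3%.

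**Step 6: after Holm over LPP and BADS at 5%.** At least one false rejection occurs when either p is below 0.025. With independent outcomes the fixed form gives 1 - 0.975² = 4.9%, and best of three gives 9.3%. Over between-outcome correlations of 0 and 0.5, the ranges are 4.6-4.9% (fixed), 5.0-6.9% (BIC), 6.4-8.7% (AIC) and 8.8-9.3% (best of three).

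**The case against.** The strongest reply is that Power speaks of a difference in slopes and the model carries a random slope, so the intended test is a 1-df linear slope x group test with other forms as checks of fit. Under that reading the transient course confirms H1 in only 2.5% of trials. Slope and week-9 tests alone disagree in about 7-11% of trials, not 18-27%. This is a plausible reading. But it comes from a power justification, while the analysis section leaves the form open and ties the verdict to whichever form results. Even a slope is not the week-9 change that H1 names.

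A second reply is that H1's wording supplies the direction. If the analyst also requires the week-9 estimate to favour Engage, the 3-df confirmation rate under the transient 0.6 SD course falls to 24-37%. That is about half, and still far above 2.5%.

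Third, nothing in the plan suggests a transient effect, and no rule selects on the interaction. Both are true. The courses are illustrations, and type I inflation is conditional: choosing the form on the time trend alone causes none. The 4.8% and 7.3% figures are worst cases under rules the plan does not state. What remains is that the rule as written excludes none of these routes.

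**Conclusion.** The concern holds and must be fixed, because the rule decides the primary hypothesis. Under forms of time that the plan expressly allows, H1 can be confirmed with no week-9 difference, and the verdict can turn on the analyst's choice of form even at the plan's own effect size. Those two conclusions follow from the wording. Their size depends on the assumed course, the covariance structure and the meaning of 0.8 SD. Type I inflation is a possibility rather than a certainty: none if the form is settled without using the arm difference, modest under BIC or AIC, and two- to threefold per outcome only under the worst-case rules.

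**What to change.** In the H1 analysis paragraph, name one confirmatory test for each of LPP and BADS: the 1-df contrast (Engage - ST) in (week 9 - baseline), from a mixed model with categorical time, group and time x group. State that H1 is confirmed for an outcome only if this contrast is significant at the multiplicity-adjusted level and favours Engage. Label slope, polynomial and omnibus interaction tests as supportive. Revise the Power sentence on slopes and conservatism to match. A prespecified linear slope test would also remove the choice of form, but it answers H1 only if the course is linear.

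The cost is SAP wording; 35 per group stands. In power:

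- On a linear course the week-9 contrast loses 4-5 points to a slope test and gains 10-13 over the 3-df test.
- If the gain comes by week 3 and holds, it gains 4-5 points over the slope test and loses 3-5 to the 3-df test.
- With an assumed random slope of SD 0.6 over 9 weeks, that last loss becomes 6-10 points (51.1 / 68.5% against 56.7 / 78.5%).

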H2. The course of LPP will be significantly associated with the course of BADS in Engage-treated participants. We will construct a mixed model for LPP as a dependent variable, similar to H1, and include BADS at concurrent assessments as a predictor. A significant effect of BADS will confirm our hypothesis.

Analyses for Secondary Hypotheses

SH1. Change in LPP for each assessment interval (baseline-3 wks, 3-6 wks) predicts severity of anhedonia at the next assessment time (6, 9 wks) in Engage, but not in ST participants. SH2. Change in BADS for each assessment interval predicts severity of anhedonia at the next assessment time in Engage, but not in ST participants. In a linear mixed effects regression, change in LPP from baseline to week 3, week 3-6, and week 6-9 will be used to predict anhedonia severity (SHAPS-C) at 3, 6, and 9 weeks. We will include fixed effects for age, time, gender, and antidepressant use. We will repeat this analysis for BADS (SH2). A significant effect for LPP or BADS will confirm our hypotheses. We chose this correlative analysis rather than a mediation analysis because we are only powered to detect a very large mediation effect.

Missing Data

The proposed mixed-model analysis provides valid inferences when data are missing at random (Hedeker & Gibbons, 2006). To assess the sensitivity of the missing-at-random assumption, we will refit these models with pattern mixture models (Little, 1993), which entails fitting separate models for different drop-out patterns, and then assessing if intervention differences are sensitive to these patterns. To determine whether overall treatment effects, adjusting for study completer status, differ from the analogous control group's estimated differences, we will also employ the pattern-mixture methodology that provides for a way of taking weighted averages of these differences. In the event that we use generalized estimating equations due to untenable distributional assumptions in mixed effect models, we will use Robins's inverse probability weighted estimator (Robins, Rotnitzky, & Zhao, 1995).

Comment on Mixed-Model Analyses

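### The secondary aim concerns change in anhedonia, but the SH1 and SH2 models predict SHAPS-C level without its baseline value, so pre-treatment severity can contribute to the coefficient

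*Combined protocol and SAP*

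**What the plan says.** - **Aim** (Aims and Hypotheses): "Secondary aim: To identify predictors of change in anhedonia with Engage".
- **Hypothesis** (same section): SH1 states that LPP change in an interval "predicts severity of anhedonia at the next assessment time (6, 9 weeks) in Engage, but not in ST participants". SH2 says the same of BADS change.
- **Model** (Analyses for Secondary Hypotheses): interval changes in LPP "will be used to predict anhedonia severity (SHAPS-C) at 3, 6, and 9 weeks". The covariates are given as "We will include fixed effects for age, time, gender, and antidepressant use", and the model is repeated with BADS for SH2.
- **Success rule** (same section): "A significant effect for LPP or BADS will confirm our hypotheses".
- **Random effects** (Comment on Mixed-Model Analyses): an age-group intercept, a subject intercept nested within it, and a random slope.
- **Other covariates** (Descriptive Statistics): variables found to be unbalanced between Engage and ST are added in comparisons of the two groups.
- **Data** (Schedule of Assessments, Arm 1): SHAPS-C is collected at baseline and at weeks 3, 6 and 9.

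**The concern.** Baseline SHAPS-C is collected but enters these models neither as part of the outcome nor as a covariate. A participant who starts very anhedonic and stays so has the same outcome values as one who worsened to that level. If people who start more anhedonic also tend to gain less LPP or BADS, the change score will be associated with later SHAPS-C even when it says nothing about how SHAPS-C moves.

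The hypotheses are confirmed by a significant coefficient alone. Part of a positive result could therefore reflect pre-treatment severity, while the stated aim would lead readers to take it as prediction of change.

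**Working it through.** The plan gives no effect size, power or sample size for SH1 or SH2, so there is no stated figure to reproduce. The check has three steps.

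**1. Text.** The aim concerns change; the hypotheses and the model concern level. Nothing else in the plan brings baseline SHAPS-C in. The imbalance rule concerns differences between arms, not differences in severity among Engage participants.

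**2. What the random intercept does.** Write SHAPS-C for person i at visit j as Y = βD + u + e, with D the change score, u the person effect and e the visit error. With k visits, the random-intercept estimate is

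β̂ = (W_DY + ψ·B_DY) / (W_DD + ψ·B_DD), where ψ = σ²e / (σ²e + k·σ²u).

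W and B are the within-person and between-person sums. B_DY includes the covariance of a person's mean D with u. The bias is therefore zero only if that covariance is zero, and it is shrunk by ψ otherwise.

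An example with assumed inputs (none is in the documents): D correlates 0.5 with baseline SHAPS-C at every interval (sign arbitrary), baseline correlates 0.7 with each follow-up, 30% of the remaining variance is shared across visits, the true effect is zero, and k = 3.

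- σ²u = 0.7² + 0.3 × 0.51 = 0.643; σ²e = 0.7 × 0.51 = 0.357
- ψ = 0.357 / (0.357 + 3 × 0.643) = 0.156
- Per person: B_DY = 3 × 0.5 × 0.7 = 1.05; B_DD = 3 × 0.25 + 0.75 = 1.50; W_DD = 2 × 0.75 = 1.50; W_DY = 0
- β̂ ≈ (0.156 × 1.05) / (1.50 + 0.156 × 1.50) = 0.164 / 1.734 = 0.095

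A simulation of this setting with 35 people gave a mean coefficient of 0.097. Without any random intercept the slope would be 0.5 × 0.7 = 0.35. The intercept removes most of the bias, but not all of it.

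**3. False confirmation.** The fits were random-intercept REML models for the Engage arm with no true effect, tested two-sided at nominal 5%. They used 32 people (35 × 0.9 = 31.5, from the 10% attrition in the Power section), both outcome windows and 1,000 replicates per setting. Severity was correlated with the individual LPP slope.

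| Assumed severity-slope correlation | Without baseline SHAPS-C | With baseline SHAPS-C |
|---|---|---|
| 0 | about nominal | about nominal |
| -0.5 to -0.7 | about 6-20% | about 5-12% |

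The variance of the LPP coefficient without adjustment, divided by that with adjustment, was 1.01-1.09.

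Further runs show how far this depends on the assumptions:

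- In 24 settings at -0.5 to -0.7 (SHAPS-C intraclass correlation 0.4-0.8, slope SD 0.3-0.5, 1,500 replicates each), the rates were 5-17% unadjusted and 5-11% adjusted. Adjustment was never worse. One example (hypothesis window, correlation -0.7, intraclass correlation 0.4, slope SD 0.5) fell from 16.9% to 10.5%.
- With correlated, autocorrelated states, the rates were 5-9% unadjusted and 5-8% adjusted.
- With 35 people and only the first-interval change tied to baseline severity, the unadjusted rates were 4-8% at a correlation of 0.3 and 6-11% at 0.5.
- A rough run with the random slope included (250 replicates, model window, correlations -0.3 to -0.7) gave about 9-14% unadjusted and 7-10% adjusted. Monte Carlo error was about 2 points and some fits gave convergence warnings.

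**The case against.** **The model matches its hypotheses.** SH1 and SH2 speak of severity, and the model predicts severity. The plan also calls the analysis correlative. This stands as far as it goes: the mismatch is with the aim. Rewording the aim alone would settle the text, but the confounding by starting level would remain.

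**The random effects already deal with it.** A reader might infer that the coefficient shows only who is more anhedonic and nothing about change. The documents do not support that. The predictor varies by interval and the plan has a subject intercept and a random slope, so only the between-person part of the coefficient is exposed to stable severity. Step 2 shows that the intercept removes much of the bias. It does not remove all of it, and the rough run with a random slope did not remove the inflation either.

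**The size is assumed.** This stands. The documents give no correlation between anhedonia severity and LPP or BADS change. A reader might take the upper end of the range as the expected error rate, but it needs a strong correlation; under other assumptions the inflation is small or absent. The rates are also before the plan's multiplicity correction.

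**Adjustment is not a cure.** This stands too. One noisy baseline score only partly captures stable severity, so false confirmation can still reach about 12%. A separate simulation in which rates returned to 4-7% after adjustment had that result largely built in, because its null assumed no association once the measured baseline was known.

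**Baseline adjustment does not target change interval by interval.** Correct, which is why the wording of the result must change with the model.

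**Conclusion.** The point holds in a limited form. The aim concerns change, the models predict level, and a baseline value scheduled for everyone is unused. Pre-treatment severity can therefore enter the LPP and BADS coefficients through their between-person part.

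There is no inflation if severity is unrelated to the change score. At assumed severity-slope correlations of -0.5 to -0.7, false confirmation is about 6-20% without baseline SHAPS-C and 5-12% with it. These ranges come from Engage-only fits without the planned random slope or age-group intercept, at nominal 5%. They were run for LPP change; SH2 has the same structure, but its size was not simulated separately.

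The case for acting does not depend on the upper figures. When severity and LPP change are unrelated, adjustment leaves the error rate about nominal, and it brings a small gain in precision. This is an improvement that should be made to a secondary analysis, not a flaw that invalidates it.

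**What to change.** 1. Add baseline SHAPS-C as a fixed covariate in the SH1 and SH2 models.
2. Report the result as association of LPP or BADS change with later anhedonia given its baseline level, and state that residual confounding by severity is possible.
3. Do not use SHAPS-C at the end of the predictor interval as the covariate. In the hypothesis window it may already reflect the LPP or BADS change; in the model window it is the outcome itself.
4. Reconcile the outcome windows. The hypotheses predict weeks 6 and 9 from the preceding interval, whereas the model predicts weeks 3, 6 and 9 from the interval ending at that visit. Baseline SHAPS-C can be added under either.

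The cost is one degree of freedom and a few sentences in the plan, with no new data collection. The return is a variance ratio of about 1.01-1.09, worth roughly 1-9% more participants for this coefficient, and a model closer to its aim.

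### SH1 and SH2 claim that prediction is specific to Engage, but the stated model and confirmation rule never compare the two arms

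*Combined protocol and SAP*

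**What the plan says.** Under Aims and Hypotheses, SH1 states that LPP change over an interval "predicts severity of anhedonia at the next assessment time (6, 9 weeks) in Engage, but not in ST participants". SH2 makes the same claim for BADS: "Change in BADS for each assessment interval predicts severity of anhedonia at the next assessment time in Engage, but not in ST participants". Both sit under a narrower heading: "Secondary aim: To identify predictors of change in anhedonia with Engage".

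Under Analyses for Secondary Hypotheses, one linear mixed regression of SHAPS-C on LPP change is described and then repeated with BADS. On the other terms the text says: "We will include fixed effects for age, time, gender, and antidepressant use". The decision rule is "A significant effect for LPP or BADS will confirm our hypotheses". Neither treatment group nor a restriction to one arm appears in the model description.

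Three other places bear on how this should be read:

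- H1, under Analyses for Primary Hypotheses, names a between-arm test: "A significant interaction between time and treatment group will confirm our hypotheses".
- H2, which concerns Engage participants only, uses wording close to that of SH1 and SH2: "A significant effect of BADS will confirm our hypothesis".
- Comment on Mixed-Model Analyses covers both arms together: "Mixed-effects models will include an age-group level random intercept to account for correlation among Engage- and ST- treated participants matched by age groups".

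**The concern.** Each secondary hypothesis has two parts: an association exists under Engage, and it does not exist under ST. The second part is a statement about the difference between arms, and nothing in the SH analysis estimates that difference. The rule asks only whether the LPP or BADS coefficient is significant and sets no condition on ST.

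Followed literally, it would let the trial report an Engage-specific predictor when the association is general to both therapies. Under a pooled fit it would do so even when the association is present only in ST. The contrast matters because the Overview chose ST as a therapy whose presumed mechanism does not act directly on the reward system. The association itself is not at risk; the label attached to it is.

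**Working it through.** **Is the between-arm test supplied elsewhere?** No.

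- The covariate lists may not be exhaustive, since H1's list also omits treatment. But H1 then makes a treatment interaction its confirming test, and the SH paragraph does not.
- Descriptive Statistics adds only variables that are unbalanced between groups.
- Comment on Mixed-Model Analyses adds only random effects.
- Missing Data speaks of differences between interventions, but the SH models define none.
- Power covers H1 and H2 only, so there is no plan figure for SH1 or SH2 to reproduce.

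**Does either reading test specificity?** No.

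- *Pooled fit.* One common slope is estimated. It can be significant with equal slopes or with a slope in ST alone. With no group term it can also reflect a treatment difference in both the change score and SHAPS-C.
- *Separate fits.* Significance in one arm and not in the other does not show that the slopes differ.

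**How large could the error be?** The following are assumptions, not plan figures: within-arm power p of 50, 70 or 80%, equal arm sizes (the plan has 35 per group), a normal approximation, a two-sided 5% level and no multiplicity adjustment.

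The within-arm noncentrality is d = z(p) + 1.96, which gives 0 + 1.96 = 1.96, 0.52 + 1.96 = 2.48 and 0.84 + 1.96 = 2.80.

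| Scenario | Formula | p = 50% | 70% | 80% |
|---|---|---|---|---|
| Pooled fit, equal slopes | P(Z > 1.96 − d√2) | 79% | 94% | 98% |
| Pooled fit, slope in ST only | P(Z > 1.96 − d/√2) | 28% | 42% | 51% |
| Separate fits, equal slopes: Engage significant, ST not | p(1 − p) | 25% | 21% | 16% |

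For p = 80%, row 1 is 1.96 − 2.80 × 1.414 = −2.00, so 98%. Row 2 is 1.96 − 2.80/1.414 = −0.02, so 51%. Row 3 is 0.80 × 0.20 = 16%.

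**Stricter threshold.** The same effects at 1.25% two-sided (assumed: 5% over four hypotheses, strictest Holm step; z = 2.498) give 61/85/93%, 13/23/30% and 21/25/24% for the three rows.

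**Second check by simulation.** Assumptions: 31 per arm (35 less 10% attrition, rounded down), within-person residual correlation 0.5, standardised slope 0.3, 2,000 runs, two-sided 5%.

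| Result | Three intervals | Two intervals |
|---|---|---|
| Pooled rule confirms, equal slopes | about 100% | 97% |
| Pooled rule confirms, slope in ST only | 70% | 49% |
| Pooled rule confirms, slope in Engage only | 70% | 49% |
| Separate fits, equal slopes: Engage significant, ST not | 6% | 17% |
| Interaction test significant, equal slopes | 5% | 6% |

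The pooled rule cannot tell an Engage-only slope from an ST-only slope. The 6% and 17% agree with p(1 − p) at the simulated within-arm power of about 94% and 77 to 78%.

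**A rule that tests the claim.** Let E and S be the standardised slope estimates in Engage and ST. Require (E − S)/√2 > 1.96 and E > 1.96. With equal slopes this is met in about 2.5% of trials at the 5% level and 0.6% at the 1.25% level. For an Engage-only effect it is met in 24/39/49% at p = 50/70/80%; the interaction alone gives 28/42/51%. At the 1.25% threshold with d = 2.80 the joint rule is met in 28%.

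**The case against.** The strongest reply is that separate fits are the natural reading. H2 leaves its restriction to Engage participants in the hypothesis sentence and does not repeat it in the model text, yet the Power section confirms it by counting only the Engage group. SH1 and SH2 follow the same pattern. The age-group random intercept is generic to all the mixed models, so it cannot show that the SH fit is pooled. On that reading the 79 to 98% and 28 to 51% figures fall away.

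This has force against relying on the pooled figures, and the text does not settle which fit is meant. It does not rescue the test: separate fits do not compare slopes, and a non-significant ST slope with 35 participants does not show absence.

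It is also fair that every percentage rests on assumed inputs, that the plan calls this analysis correlative, that H1 is unaffected, and that an association within Engage would meet the secondary aim. These points limit the consequence and leave the gap in place.

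Two related matters need settling separately. The plan names both Holm and Benjamini-Hochberg for multiplicity. The hypotheses also predict anhedonia at weeks 6 and 9, while the model uses weeks 3, 6 and 9.

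**Conclusion.** The concern holds. As written, SH1 and SH2 can be declared confirmed without any comparison of the arms, so the Engage-specific part of each claim is untested under either reading. That conclusion rests on the text alone.

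The size depends on assumptions the plan does not supply. With equal slopes, the wrong label would follow in about 16 to 25% of trials under separate fits at 50 to 80% within-arm power (6 to 17% in the simulated settings), and in 79 to 98% under a pooled fit. The hypotheses are secondary and the association stays reportable, so this should be corrected but does not threaten the primary analysis.

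**What to change.** 1. Add treatment group and group-by-LPP-change to the SH1 model, and treatment group and group-by-BADS-change to the SH2 model.
2. Replace the confirmation rule with: *A stronger association in Engage than in ST is concluded only if the interaction is significant in that direction and the Engage slope is significant, after the plan's multiplicity adjustment; otherwise only an association is reported.*
3. Report the slope in each arm with its confidence interval in all cases. This also exposes an ST slope of opposite sign, where the rule would show that the slopes differ but not that the Engage association is larger in size.
4. Reword SH1 and SH2 to say that change predicts anhedonia more strongly in Engage than in ST. A significant interaction does not show absence in ST: with assumed noncentralities of 5.6 in Engage and 2.8 in ST, the joint rule is met in 51% of trials, and in 33% of trials it is met with ST also significant.

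The cost is two model terms per hypothesis, one decision rule and a rewording, with no new data. The drawback is the limited power shown above: about 49% at the 5% level, or 28% at 1.25%, for an Engage-only effect with 80% within-arm power at 5%. The team should expect that the claim may have to stop at an association.
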